## 4 STUDY DESIGN

This is a single-center, unblinded, study in which healthy infants and children (6 weeks – 24 months inclusive) will have placebo microneedle patches applied to the skin. This study is designed to investigate the safety, reactogenicity, and acceptability of a placebo microneedle patch.

Infants and children will be recruited from metropolitan Atlanta and will be enrolled at Emory Children's Center. Approximately 25 to 50 infants and young children will be enrolled into one of two possible cohorts that will have placebo microneedle patches administered topically for up to approximately 20 minutes. Cohort 1 will assess one formulation of the microneedle patch (Microneedle Formulation 1). If the Microneedle Formulation 1 is well tolerated in Cohort 1, Cohort 2 may be enrolled using a different formulation of the microneedle patches if available (Microneedle Formulation 2).

After informed consent is obtained, subjects will be screened by history and physical examination at screening. Collected data will include demographic information, medical history, list of current and recent medications, and vaccination history. The placebo microneedle patch will be administered on Day 1 to subjects meeting enrollment criteria. Each subject will have 3 clinic visits: Day 1, Day 2 (+1 day), and Day 8 (+2 days). One telephone call will occur (Day 29 +/- 3 days). In those that receive additional microneedle patches on Day 8 (+2 days), follow-up visits will also occur at Day 9 (+2 days) and Day 15 (+3 days). Refer to the Appendix A for a detailed listing of study days and procedures.

Safety will be measured by the occurrence of solicited application site and systemic reactogenicity on the day of microneedle patch administration through Day 8 (+2 days) for the first patch and through Day 15 (+3 days) for the second and third patch. Unsolicited AE, and serious adverse events (SAEs) and new-onset medical conditions (NOMC) will be collected through Day 29 and Day 38 after microneedle patch administration. The acceptability of applying a microneedle patch topically will be assessed by LAR survey completed before microneedle patch application on Day 1, after microneedle patch removal on Day 1, at Day 2 (+1 day), Day 8 (+2 days), and the Final Study Visit (Day 27 – 38) in everyone. In those that receive additional microneedle patches, it will be also be repeated at Day 9 (+2 days) and Day 15 (+3 days).

Infants and children will be enrolled by sequential age groups using an age de-escalation approach (Table 1). At least 4 infants or children from each Group must complete Day 8 without halting criteria having been met (as detailed in Section 9.5) before subjects will be enrolled into the next younger age group within a Cohort. For Cohort 1, at least the first 2 children in each Group will have the microneedle patch applied to the skin overlying the shoulder blade. If this site is well tolerated without halting criteria having been met (as detailed in Section 9.5), additional microneedle patches may be applied at a different location on the same participant and in subsequent participants to the upper arm, forearm, wrist, thigh, shin, and/or foot. For Cohort 2, microneedle patches may be applied to the

shoulder blade, upper arm, forearm, wrist, thigh, shin, and/or foot. If the first site is well tolerated in the first two children without halting criteria having been met (as detailed in Section 9.5), additional microneedle patches may be applied to the same participants and in subsequent participants.

Table 1: Cohorts and Groups of Enrolled Infants and Young Children			
Cohort	Group Age Range*	Number **	Study Product (administered Day 1 and possibly Day 8)
1	12 – 24 months	Up to 7	Microneedle formulation 1
1	5 – 11 months	Up to 6	Microneedle formulation 1
1	6 weeks – 4 months	Up to 12	Microneedle formulation 1
2	12 – 24 months	Up to 12	Microneedle formulation 2
2	5 – 11 months	Up to 12	Microneedle formulation 2
2	6 weeks – 4 months	Up to 12	Microneedle formulation 2

*\*All age ranges are inclusive. 4 children from each age group must complete Day 8 without halting criteria having been met (as detailed in Section 9.5) before subjects will be enrolled into the next younger age group.*

*\*\* Total number enrolled into each Cohort will be ≤25.*

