**Schematic of Study Design:**

This is a single-center, unblinded, study in which healthy infants and children (6 weeks – 24 months inclusive) will have placebo microneedle patches applied to the skin. This study is designed to investigate the safety, reactogenicity, and acceptability of a placebo microneedle patch.

Infants and children will be enrolled into one of two possible cohorts that will have placebo microneedle patches administered topically for up to approximately 20 minutes. Cohort 1 will assess one formulation of the microneedle patch (Microneedle Formulation 1). If the Microneedle Formulation 1 is well tolerated in Cohort 1, Cohort 2 may be enrolled using a different formulation of the microneedle patch if available (Microneedle Formulation 2). Infants and children will be enrolled by sequential age groups using an age de-escalation approach (**Table 1**). At least 4 infants or children from each Group must complete Day 8 without halting criteria having been met (as detailed in Section 9.5) before subjects will be enrolled into the next younger age group within a Cohort. For Cohort 1, at least the first 2 children in each Group will have a microneedle patch initially applied to the skin overlying the shoulder blade. If this site is well tolerated without halting criteria having been met (as detailed in Section 9.5), additional microneedle patches may be applied to the same participants and in subsequent participants to the upper arm, forearm, wrist, thigh, shin, and/or foot. For Cohort 2, microneedle patches may be applied to the shoulder blade, upper arm, forearm, wrist, thigh, shin, and/or foot. If the first site is well tolerated in the first two children without halting criteria having been met (as detailed in Section 9.5), additional microneedle patches may be applied to the same participants and in subsequent participants.

Table 1: Cohorts and Groups of Enrolled Infants and Young Children			
Cohort	Group Age Range*	Number **	Study Product (administered Day 1 and possibly Day 8)
1	12 – 24 months	Up to 7	Microneedle formulation 1
1	5 – 11 months	Up to 6	Microneedle formulation 1
1	6 weeks – 4 months	Up to 12	Microneedle formulation 1
2	12 – 24 months	Up to 12	Microneedle formulation 2
2	5 – 11 months	Up to 12	Microneedle formulation 2
2	6 weeks – 4 months	Up to 12	Microneedle formulation 2

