### **5.4.3 Handling of Withdrawals**

The LAR(s) of an infant or young child will be informed that they have the right to discontinue their child's study participation at any time without prejudice. Although the LAR(s) are not obligated to state the reason for withdrawal, every attempt should be made to establish if the reason for discontinuation is due to the study product or an AE. LAR(s) who withdraw their child for any reason should be asked to complete an Early Termination Visit.

Ongoing AEs or reactogenicity should be followed to resolution if the LAR is agreeable to continued phone contact by the study staff. Subjects who are withdrawn from the study

for any reason will not be replaced, unless there are fewer than 4 subjects who have reached Day 8 for any given age group.

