### 11.2 Sample Size Considerations

For sample size calculation and statistical analysis plan the primary and secondary endpoints will mainly be addressed. The small numbers in this study allow only rough estimates of safety. With 25 subjects per cohort, if the true event rate is 5%, we will have 34% chance to observe one AE and 12% chance to observe more. If the true event rate is 10%, the chance to observe one AE is 38%, and the chance to observe more than one AEs is 34%.

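### Do the Cohort 2 age-group ceilings (12/12/12 under a cap of 25) wrongly leave the youngest infants on Formulation 2 with only 1 assured place?

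*Combined protocol and SAP*

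**What the plan says.** Table 1 appears in the Protocol Summary and again in Section 4. It sets a maximum for each age group: 7, 6 and 12 in Cohort 1, and 12, 12 and 12 in Cohort 2, from oldest to youngest. The column heading points to a footnote: "Total number enrolled into each Cohort will be ≤25".

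The order of enrollment is fixed in Section 4: "Infants and children will be enrolled by sequential age groups using an age de-escalation approach". The step-down rule there reads "At least 4 infants or children from each Group must complete Day 8 without halting criteria having been met", and the Protocol Summary continues it as "before subjects will be enrolled into the next younger age group within a Cohort".

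Cohort 2 is conditional on Formulation 1 being well tolerated: "Cohort 2 may be enrolled using a different formulation of the microneedle patches if available". Under Section 5.4.3, subjects who are withdrawn "for any reason will not be replaced, unless there are fewer than 4 subjects who have reached Day 8 for any given age group". Section 11.2 frames its chances of observing events by cohort, beginning "With 25 subjects per cohort, if the true event rate is 5"%.

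**The concern.** The two cohorts look inconsistent. In Cohort 1 the maxima add up exactly to the cap, so 12 places stay open for the youngest group however the older groups fill. In Cohort 2 the maxima exceed the cap by 11, and oldest-first enrollment puts any shortage on the youngest group. Read literally, the maxima keep only 1 place open for infants of 6 weeks to 4 months.

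No other text holds places for them. The rule of 4 completers governs the move to the next younger group, so it sets no number for the last one. The replacement rule deals with withdrawals and reserves nothing.

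Cohort 2 is the only source of data on Formulation 2. If the youngest group were cut to 1–3 infants, the study would say almost nothing about that formulation at that age, yet the cohort would still match the per-cohort sample-size statement.

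**Working it through.** **Inputs.** Maxima and cap from Table 1; step-down rule from Section 4; replacement rule from Section 5.4.3; sample-size statement from Section 11.2; analyses from Section 11.3.

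**1. Maxima against the cap.**
- Cohort 1: 7 + 6 + 12 = 25, equal to the cap. Places always left for the youngest: 25 − (7 + 6) = 12.
- Cohort 2: 12 + 12 + 12 = 36, which is 11 above the cap. Places always left for the youngest: 25 − (12 + 12) = 1.

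These figures are correct. They describe ceilings and a separate total; the actual split is whatever meets both.

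**2. Which full Cohort 2 allocations are permitted.** Let a and b be the numbers in the two older groups, each from 4 to 12, and c = 25 − a − b with c between 0 and 12. There are 9 × 9 = 81 pairs (a, b). The 15 pairs with a + b of 12 or less would need c above 12 and drop out, leaving 66.
- c = 1: 12/12/1
- c = 2: 12/11/2 and 11/12/2
- c = 3: 12/10/3, 11/11/3 and 10/12/3

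So 6 allocations leave 1–3 places and 60 leave at least 4. This is a count, not a probability, and totals below 25 are also allowed.

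**3. What it takes to reach those six.** The step-down rule needs 4 completers in each older group, 8 in all. Leaving 1–3 places requires 22 to 24 older children, which is 14 to 16 more than that minimum (assuming no withdrawals). The site keeps 4 places open if the older groups total at most 25 − 4 = 21, and all 12 if they total at most 25 − 12 = 13, the same 13 as in Cohort 1. The plan as written allows both.

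**4. What small numbers would mean.** Chance of at least one event at a true 10% rate: 1 − 0.9^n. Upper limit after zero events: 1 − 0.025^(1/n) for the upper end of the exact two-sided 95% interval, and 1 − 0.05^(1/n) for the one-sided 95% limit.

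| n | At least one event at 10% | Upper limit, two-sided | Upper limit, one-sided |
|---|---|---|---|
| 1 | 10.0% | 97.5% | 95.0% |
| 2 | 19.0% | 84.2% | 77.6% |
| 3 | 27.1% | 70.8% | 63.2% |
| 4 | 34.4% | 60.2% | 52.7% |
| 12 | 71.8% | 26.5% | 22.1% |

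One to three infants are indeed uninformative by themselves. But even the maximum of 12 leaves a true rate of more than one in five compatible with no events, so no permitted allocation gives a precise estimate for this age group.

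**5. Does any stated purpose depend on the youngest group's size?**
- Objectives and endpoints (Section 3, repeated in 11.1): none is defined by age.
- Sample size (Section 11.2): per cohort, and expressly for rough estimates of safety.
- Analysis (Section 11.3): descriptive counts and percentages by treatment group in the safety population. Product differs by cohort, not by age.

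No planned result fails or changes meaning under an uneven age split.

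**The case for a change.** The strongest case for the concern is that the protection in Cohort 1 is automatic, while in Cohort 2 it depends on the site's discretion. Nothing obliges the site to step down after 4 completers, and recruitment to an older group may continue while Day 8 visits are awaited. Section 2.3.2 says the results will inform a planned poliovirus vaccine trial in infants, so young-infant data have a stated use. The replacement rule applies "unless there are fewer than 4 subjects who have reached Day 8 for any given age group", which suggests that 4 per group was regarded as meaningful; six permitted allocations cannot supply that number in the youngest group. Finally, the chances printed in Section 11.2 (34% and 12% at a 5% rate; 38% and 34% at 10%) do not reproduce at n = 25, where one event and more than one have chances of 36.5% and 35.8%, then 19.9% and 72.9%. They do reproduce at n = 12 (34.1% and 11.8%; 37.7% and 34.1%).

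The discretion is real, and a line stating a minimum would remove it. The rest carries less weight:
- The contrast with Cohort 1 concerns places held open, not infants enrolled. Its numbers are also maxima under a total of 25 or fewer, so a Cohort 1 with 1–3 youngest infants is equally permitted.
- The planned vaccine trial is described as in infants, without singling out 6 weeks to 4 months.
- If 4 per group was the working expectation, the site can meet it under the present text.
- The figures in Section 11.2 are a separate matter. They cannot be read as a promise of 12 per age group: Cohort 1 limits its two older groups to 7 and 6, and three groups of 12 cannot fit under 25.

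**Conclusion.** The concern does not hold. The sums are right: 36 against a cap of 25, 1 place always left against 12 in Cohort 1, and 6 of 66 full allocations leaving 1–3 places. But Table 1 openly combines per-group ceilings with a footnoted total, and that is not a contradiction. The thin youngest group arises only if the site enrolls 22–24 older children when 8 completers allow it to move on, and the site can avoid this without an amendment. No objective, endpoint, sample-size statement or analysis rests on the number of youngest infants, so the plan followed as written still yields the descriptive per-cohort summary that it promises.

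Fixing the split or reserving places would give up places for older children and some flexibility, and would still not ensure that any infant is enrolled. That is a trade-off for the sponsor, and it arises only if Cohort 2 opens. This conclusion assumes that treatment group in Section 11.3 means formulation rather than age group, and that no age-specific claim about Formulation 2 is intended beyond what the protocol states.

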## 5 STUDY POPULATION

### 5.1 Selection of the Study Population

Approximately 25 or 50 healthy male and female infants and young children will be enrolled. The study will be conducted at a single site. Subjects will be recruited from the community at large.

Only infants and young children who meet the inclusion/exclusion criteria will be eligible for enrollment into this study.

### 5.2 Subject Inclusion Criteria

A subject must meet all the following criteria to be eligible to participate in this study:

1. LAR provides written informed consent prior to any study procedures being performed.
2. Subject is between the ages of 6 weeks and 24 months, inclusive, on the day of signing informed consent.
3. Subject is in good health as determined by vital signs, medical history, and a targeted physical examination.
4. LAR is able to understand and comply with required study procedures.

### 5.3 Subject Exclusion Criteria

A subject will not be eligible to participate in this study if any the following criteria apply:

1. Subject has an acute illness with fever (temperature >100.4 °F) within 72 hours prior to enrollment.
2. Subject has a known chronic medical problem.
3. Subject has known immunosuppression due to underlying illness or treatment, including (but not limited to): Human Immunodeficiency Virus (or birth to a HIV-positive mother), hepatitis B or C; organ transplant; active cancer or any history

of hematologic cancer; receipt of chemotherapy or radiation therapy; congenital immunodeficiency, anatomical or functional asplenia.

4. Subject has used long-term\* high-dose\*\* oral or parenteral glucocorticoids, or high-dose inhaled steroids.\*\*\*

*\* Long term is defined as taken for 2 weeks or more in total at any time during the past 2 months.*

*\*\* High dose defined as prednisone  $\geq$  20 mg total daily dose, or equivalent dose of other glucocorticoids.*

*\*\*\* High dose defined as  $>800$  mcg/day of beclomethasone dipropionate or equivalent.*

5. Subject has a history of an underlying skin condition (e.g., eczema, atopic dermatitis) or an open lesion (e.g., laceration, abrasion), scar, or rash in the areas of the planned microneedle patch administration which will interfere with the assessment of reactogenicity.
6. Subject or family members have a history of keloid formation.
7. Subject has any condition that, in the opinion of the investigator, may put the subject at increased risk of harm, may cause the subject to be unable to meet the requirements or might otherwise interfere with evaluations required by the study.
8. Subject has received any experimental products within 30 days before study entry or plan to receive experimental products at any time during the study.
9. Subject has received a vaccine within 7 days of enrollment or plans to receive a vaccine within 7 days after enrollment.
10. Subject has previously received immunoglobulin or blood products.

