#### Optional Microneedle Patch 2/3 Study Events Day 8 (+2 days)

- The optional consent for the optional placebo microneedle patches 2/3 will be signed before additional study procedures occur on Day 8 (if not already signed).
- Inclusion/Exclusion criteria review.
- A baseline photograph of the area of application may be obtained.

- Application of placebo microneedle patches 2/3 to the skin in a different location than previously by a trained study nurse. The placebo microneedle patches will remain in place for up to 20 minutes. The patches will then be removed and the used patch will be saved.
- The memory aid, thermometer and ruler will be provided to the LAR and instructions will be provided.
- The site of the placebo microneedle patches removal will be assessed at least 15 minutes and 30 minutes post-placebo microneedle patch removal. Per investigator discretion, photographic documentation (refer to MOP) and dermatologic referrals may be obtained.
- Study personnel will assess and record all AE/SAEs that occur after enrollment.
- The acceptability questionnaire will be completed by the LAR.

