#### **8.1.2 Concomitant Medications**

All medications including prescriptions, over-the-counter medications, vitamins and supplements taken by the subject in the 30 days prior to enrollment should be recorded at the screening visit. Assessment of eligibility will also include a review of permitted and prohibited medications per the exclusion criteria. At subsequent visits, LAR(s) will be queried about changes in their infant or young child's medications. Each new concomitant medication or change to existing medication will be recorded through the Final Study Visit (Day 27 – 38).

Medications which may interfere with the evaluation of the investigational product should not be used during the study unless absolutely necessary. Medications or treatments which are prohibited include:

- Vaccines (unless clinically necessary, vaccines should be avoided within 7 days of enrollment. Live vaccines should not be administered during the study).
- Oral, parenteral or high-dose inhaled steroids.
- Immunosuppressive or cytotoxic therapy.
- Blood products or immunoglobulins.
- Experimental products.

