### **8.1.5 Reactogenicity**

The LAR will be provided with a memory aid, thermometer and ruler and will be instructed to record the presence of solicited symptoms and oral temperature through the Day 8 (+2 days) (Day 15 +3 days in those having microneedle patches 2/3 placed).. If a symptom is still present at that time, the LAR will continue to follow that symptom until two days symptom-free. Memory aids will be reviewed and collected by study staff at follow-up visits.

Solicited local microneedle patch application site symptoms include:

- Pain
- Erythema
- Ecchymosis (bruising)
- Induration/swelling
- Pruritus (itching)
- Tenderness

Solicited systemic reactions include:

- Fever
- Irritability (fussiness) above baseline
- Lethargy (drowsiness)
- Decreased appetite
- Vomiting

The LAR will use the following grading scale for describing symptoms:

- Grade 0: Not present
- Grade 1: Mild (present but easily tolerated)
- Grade 2: Moderate (able to tolerate routine activity with effort)
- Grade 3: Severe (unable to continue routine activity)

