## 14 SUPPLEMENTS/APPENDICES

### 14.1 Appendix A: Study Schedule

Visit #	1	2	3	4 &	5 &	Final*		
Procedures	D1	D2 +1	D8 +2	D9 +2	D15 +3	D27 - D38	Unscheduled Visit (If needed)	Premature Discontinuation
Signed Consent Form	X							
Inclusion/Exclusion Review	X							
Complete Medical History	X							
Concomitant Medications	X	X	X	X &	X &	X	X	X
Interim Medical History		X	X	X &	X &	X	X	X
Sign Optional Consent For Microneedle Patch 2/3	(X )		(X)					
Application of microneedle patch	X		X &					
Distribute memory aid, ruler & thermometer	X		X &					
Review memory aid		X	X	X &	X &	(X)	(X)	(X)
Physical Exam	Complete Physical Exam	X						
	Assessment of microneedle patch application site	X* *	X	X* *&	X &	X &	X	X
	Symptom-Directed Physical Exam		(X)	(X)	(X) &	(X) &	(X)	(X)
	Height and weight	X						
	Vital Signs ^	X	X	X	(X) &	(X) &	X	X
Photograph site of placebo microneedle patch	(X )	(X)	(X)	(X)	(X)	(X)	(X)	(X)
Assessment of Adverse Events and SAEs	X* *	X	X	(X) &	(X) &	X	X	X
Acceptability Questionnaire	X	X	X	(X) &	(X) &	X	X	X

\* The final study visit will be a telephone call at D27 – D38

\*\* Occurring 15 minutes and 30 minutes after microneedle patch removal.

& At Day 8 the LARs of subjects who no ongoing solicited or unsolicited general AE or local AEs will have the opportunity to decide to have second and third placebo microneedle patches placed at different body sites from the initial location. In those that elect to have a second/third placebo microneedle patch placed, they will return for clinic visits on Day 9 and Day 15.

^ Vital signs will include temperature and pulse.

(X) – As indicated/appropriate.

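### The 7-day vaccine restriction counts from enrollment, so the eight days after optional patches 2/3 have almost no explicit non-live vaccine interval

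*Combined protocol and SAP*

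**What the plan says.** Two places limit vaccination, and both count from enrollment.

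- Section 5.3, item 9 excludes a child if "Subject has received a vaccine within 7 days of enrollment or plans to receive a vaccine within 7 days after enrollment".
- Section 8.1.2 opens with a general rule that medications which may interfere with the evaluation "should not be used during the study unless absolutely necessary". It then lists vaccines among the prohibited treatments, with their own parenthesis: except for clinical need, "vaccines should be avoided within 7 days of enrollment. Live vaccines should not be administered during the study".

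Section 7.1 makes enrollment and patch 1 the same day, Day 1. Section 7.3 allows optional patches 2 and 3 at the Day 8 (+2) visit and calls for an "Inclusion/Exclusion criteria review" beforehand. Appendix A, as extracted, marks "Inclusion/Exclusion Review" on Day 1 only.

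Both primary solicited endpoints in Section 3.2.1 cover eight days from patch application. In Section 8.1.5, the list headed "Solicited systemic reactions include" comprises fever, irritability, lethargy, decreased appetite and vomiting. For patches 2/3, Sections 9.2.1 and 9.2.2 end solicited collection at Day 15. The Protocol Summary, Section 4 and Section 8.1.5 say Day 15 (+3).

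**The concern.** The rule matches the endpoint window of patch 1 exactly and then lapses as patches 2/3 go on. No reason is given for protecting one application and not the others. Because only live vaccines are barred for the whole study, non-live vaccines appear to be acceptable after about Day 8.

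The study has no control group. A vaccine given in the week after patches 2/3 can plausibly cause the same systemic signs that are being solicited. The investigator must then make a two-way related/unrelated call (Section 9.2.1), and that call decides whether a Grade 3 event enters the primary safety endpoint. A fever above 102.1 F is Grade 3 in Appendix C. After a vaccine, such a fever could be counted against the patch, or it could be set aside so that a patch effect is missed. Under Section 9.5, a single Grade 3 event without a clear other cause halts enrollment and further patching. Section 11.3 plans no listing or summary that takes vaccination into account.

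**Working it through.** **Inputs.** Enrollment and patch 1 on Day 1 (Section 7.1). Restriction of 7 days after enrollment (5.3 item 9, 8.1.2). Patches 2/3 on application day A = 8, 9 or 10 (7.3). Endpoint window of 8 days (3.2.1). Visit 5 on Day 15 (+3), that is Days 15 to 18 (7.5).

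**Counting convention, checked on patch 1.** Day 1 through Day 8 inclusive is 8 − 1 + 1 = 8 days. This reproduces the plan's 8-day window, so the application day counts as the first day and the window for any patch is A to A + 7.

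**Restriction.** It ends on Day 1 + 7 = Day 8. For patch 1 the window is Days 1–8, so 0 of 8 days are open.

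**Patches 2/3.** Open days are the window days after Day 8:

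| Applied | Window | Open to non-live vaccine | Open in the 7 days before |
|---|---|---|---|
| Day 8 | Days 8–15 | Days 9–15 = 7 of 8 | Days 1–7: 0 |
| Day 9 | Days 9–16 | Days 9–16 = 8 of 8 | Days 2–8: 0 |
| Day 10 | Days 10–17 | Days 10–17 = 8 of 8 | Days 3–9: 1 (Day 9) |

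The gap therefore lies almost entirely after the application.

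**Sensitivity to the convention.** If the restriction is read as ending on Day 7, or if the application day is not counted, a Day 8 application also has 8 of 8 days open. So 7 of 8 is the lower bound. Under either of those readings patch 1 would have one open day (Day 8 or Day 9 respectively).

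**After re-anchoring.** A restriction from A to A + 7 ends on Day 15, 16 or 17 and leaves 0 of 8 days open in each case.

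**Minor point: solicited collection.** A fixed Day 15 end covers 15 − A + 1 days, which is 8, 7 or 6 of the 8 endpoint days for A = 8, 9 or 10. Under Day 15 (+3), all 8 days are covered if Visit 5 falls on or after Day 16 (A = 9) or Day 17 (A = 10). Both fit within Days 15–18.

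**The case against.** The strongest reply is that the plan already handles this at the patch 2/3 visit. Section 7.3 repeats the eligibility review. Read literally, that review would also ignore a current fever, because item 1 refers to enrollment too, so a sensible reader re-dates the criteria to the new application. Item 7 lets the investigator exclude a child for anything that would interfere with evaluations. The general sentence in 8.1.2 covers the whole study, and its seven-day parenthesis can be read as added guidance rather than as a replacement. The single mark in Appendix A carries little weight against the plain text of 7.3.

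Much of this stands. The check exists, and a careful site may defer a vaccine. But none of these provisions states an interval after patches 2/3, and barring only live vaccines throughout points the other way for non-live ones.

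It is also fair that the harm needs several steps: optional patches, a non-live vaccine in that week, a systemic event, and a wrong call. A known vaccine is itself an alternative cause that the investigator may name under the halting rule. Section 8.1.2 provides that "Each new concomitant medication or change to existing medication will be recorded through the Final Study Visit", so vaccines should already be captured. The existing rule is soft even for patch 1, because of its clinical-need exception.

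A reader might infer that both primary endpoints are exposed. The documents do not support that. Application-site reactions are judged at the patch site and are little affected, unless a vaccine is given at the same site. A reader might also infer that solicited follow-up of patches 2/3 is cut short. That is certain only under the plain Day 15 wording of 9.2.1 and 9.2.2 with a Day 9 or 10 application. The Day 15 (+3) text elsewhere largely meets it, and unsolicited events are collected to the final call in any case.

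**Conclusion.** The point holds as a rule with the wrong anchor. Patches 2/3 have no explicit non-live vaccine interval on 7 of 8 endpoint days (Day 8 application) or 8 of 8 (Day 9 or 10), against 0 of 8 for patch 1, subject to the clinical-need exception. The consequence is limited to solicited systemic events, their relatedness call and the Grade 3 halting rule, in children who receive the optional patches.

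This rests on two readings: that the application day is the first of the eight days, and that the eight-day endpoints apply to each patch. The extended solicited collection for patches 2/3 supports the second.

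A reader might turn the day counts into a likelihood of confounding. The documents do not allow it, because they give neither a vaccination rate nor the uptake of optional patches. With an assumed rate v among n recipients, the chance of at least one vaccinated child is 1 − (1 − v)^n. That is 1 − 0.98^10 = 18% for v = 2% and n = 10, and 1 − 0.90^25 = 93% for v = 10% and n = 25. A range that wide reflects only the assumptions. It is also the chance that a child is vaccinated in the window, not that an endpoint is misclassified.

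**What to change.** - In 5.3 item 9 and 8.1.2, apply the seven-day criterion relative to each patch application (enrollment and patches 2/3). Keep the clinical-need exception.
- State in 7.3 that it is checked at the Day 8 review, and mark that review in Appendix A. A child with a vaccine due either skips the optional patches or has the vaccine briefly deferred.
- In 11.3, if a vaccine is given in a patch 2/3 window, list that child's solicited systemic events with the vaccine date, using the concomitant medication data. A listing is enough; with at most 25 children per cohort a split table would add little.
- Minor: in 9.2.1 and 9.2.2, end solicited collection seven days after the actual application day (Day 15, 16 or 17), and hold Visit 5 no earlier than that day.

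The cost is protocol wording and one eligibility check. No visits or subjects are added, and memory aids run up to two days beyond Day 15 for late applications. Some optional-patch recipients, and therefore some body-site data, may be lost, or some vaccines delayed by a few days. The documents do not show how many.
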